10.2 Analysis of Adverse Events

A treatment-emergent Adverse Event (TEAE) is defined as an adverse event with an onset date that is after the first dose of study drug, and no more than 30 days or 5 half-lives of the drug, whichever is larger, after the last dose of study drug. Specifically, 30 days will be used for Upadacitinib and placebo, and 70 days will be used for ADA.

Events where the onset date is the same as the study drug start date are assumed to be treatment-emergent, unless the study drug start time and the adverse event start time are collected and the adverse event start time is prior to the study drug start time. If an incomplete onset date was collected for an adverse event, the event will be assumed to be treatment-emergent unless there is other evidence that confirms that the event was not treatment-emergent (e.g., the event end date was prior to the study drug start date).

Adverse event data will be presented by SOC and PTs using MedDRA version 19.0 or most up to date version. All adverse event tables will be sorted in alphabetical order by SOC and PT and descending percentages for each treatment group.

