### 6.1.4 Adverse Event Collection Period

All AEs reported from the time of study drug administration until 70 days following discontinuation of subcutaneous study drug administration and until 30 days following the discontinuation of oral study drug administration have elapsed will be collected, whether solicited or spontaneously reported by the subject. Subjects who discontinue study drug treatment but continue to participate in the study will have SAEs and non-serious AEs collected for the remainder of the study participation. In addition, SAEs and protocol-related nonserious AEs will be collected from the time the subject signed the study-specific informed consent.

Adverse event information will be collected as shown in [Figure 5](#).

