#### **8.1.5.2.1 Treatment-Emergent Adverse Events (TEAE)**

AEs will be coded using MedDRA. A TEAE is defined as AE that began or worsened in severity after initiation of study drug.

AEs starting more than 70 days following the last dose of study drug for subjects on ADA and AEs starting more than 30 days following the last dose of study drug for subjects on upadacitinib or placebo will not be included in summaries of TEAEs. For subjects who continued into Period 2, the AEs that are reported in Period 2 will be summarized in the long term safety analysis.

As a general safety summary, the number and percentage of subjects experiencing TEAEs will be summarized for each treatment group for the following AE categories:

- All AEs;
- All severe AEs;
- All reasonably possibly related AEs;
- All SAEs;
- Frequent AEs (reported in 2% of subjects or more in any treatment group);
- Frequent reasonably possibly related AEs (reported in 2% of subjects or more in any treatment group);
- Discontinuations due to AEs;
- Death.

Additional AEs may be considered for tabulation/summary based on recommendations from Clinical and Safety as deemed appropriate.

TEAEs will be summarized and presented by system organ classes (SOCs) and preferred terms (PTs) using MedDRA. The SOC's will be presented in alphabetical order, and the PTs will be presented in alphabetical order within each SOC.

TEAE will also be summarized by maximum severity and by maximum relationship.

The AEs of special interest (including but not limited to serious infection, opportunistic infection, herpes zoster, TB, gastrointestinal perforations, malignancies, MACE, renal dysfunction, anemia, increased CPK, non-cardiac, non-CNS embolic and thrombotic events, and drug-related hepatic disorders) will be summarized. Event rate (per 100 patient years) for AEs of special interest will also be summarized for the combined safety analysis of Period 1 and Period 2.

All AEs leading to discontinuation of study drug will be presented in listing format. A listing by treatment group of TEAEs grouped by SOC and MedDRA preferred term with subject identification numbers will be generated.

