8.0 Study Drug Exposure and Compliance

8.1 Study Drug Exposure

The duration of exposure to study drug will be summarized for the safety analysis set by the following groups. Subjects could switch to another treatment at Week 14 or later per study design. For subjects switching treatments, the exposure under the new study drug begins on the day when the new therapy is initiated, and the exposure under the previous study drug ends on the day before.

The duration of exposure to study drugs will be summarized by the following groups.

1. Placebo
2. ADA 40 mg EOW

This includes ADA exposure from subjects starting on ADA 40 mg EOW and subjects who switched from Upadacitinib 15 mg QD to ADA 40 mg EOW.

3. Upadacitinib 15 mg QD

This includes Upadacitinib 15 mg QD exposure from subjects starting on Upadacitinib 15 mg QD, subjects who switched from placebo to Upadacitinib 15 mg QD, and subjects who switched from ADA 40 mg EOW to Upadacitinib 15 mg QD.

The duration of exposure to study drug will be summarized for each group as specified above, with the number of subjects, mean, standard deviation, median, minimum and

maximum values. In addition, the number and percentage of subjects exposed to study drug will be summarized for the following cumulative duration intervals.

- ≥ 2 weeks
- ≥ 1 month
- ≥ 3 months
- ≥ 6 months
- ≥ 9 months
- ≥ 12 months
- ≥ 18 months
- ≥ 2 years
- ≥ 2.5 years
- ≥ 3 years
- ≥ 4 years

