10.2.2.1 Overview of Adverse Events Rates per 100 Patient-Years of Study Drug Exposure

An overview of AEs per 100 patient-years of study exposure will be presented by treatment group and overall for the following AE categories.

- All TEAEs
- Treatment-emergent serious adverse events (SAEs)
- Treatment-emergent severe adverse events
- TEAEs reasonably possibly related to study drug

- TEAEs of special interest
- TEAEs leading to discontinuation of study drug
- TEAE leading to death

For this calculation, one year will be considered to be 365.25 days. For each treatment group, the numerator of the overall rate will be the total number of TEAEs reported for the event; that is, a subject can contribute more than one event to the numerator. For each treatment group, the denominator of the rates will be the total number of days exposed to study drug summed across all treated subjects divided by 365.25. Please refer to Section 6.0 for the calculation of study drug exposure. The AE rate per 100 patient-years of exposure will be calculated as $(\text{[numerator/denominator]}) \times 100$. The number of AEs reported (numerator), the total number of years of study drug exposure (denominator), and the AE rate per 100 patient-years will be presented for each treatment group and overall.

Additional AEs may be considered for tabulation/summary based on recommendations from Clinical and Safety as deemed appropriate.

For TEAEs of special interest, the point estimate and 95% CI (using normal approximation) will be provided for the treatment difference in AE rates per 100 patient-years.

10.2.2.2 Adverse Events Rates per 100 Patient-Years of Study Drug Exposure by SOC and PT

For each treatment group, the TEAE rate per 100 patient-years of exposure will be calculated overall, for each SOC and each PT, for each of the following events:

- All TEAEs
- Treatment-emergent serious adverse events (SAEs)
- Treatment-emergent severe adverse events
- TEAEs reasonably possibly related to study drug
- TEAEs leading to discontinuation of study drug
- TEAE leading to death

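### Long-term adverse event rates count events after the last dose (70 days for adalimumab, 30 for upadacitinib and placebo) but leave that time out of the patient-years

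*SAP*

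**What the plan says.** SAP 10.2 defines a treatment-emergent event as one starting after the first dose and "no more than 30 days or 5 half-lives of the drug, whichever is larger, after the last dose of study drug". It then fixes the figures: "30 days will be used for Upadacitinib and placebo, and 70 days will be used for ADA". Protocol 8.1.5.2.1 has the same split and leaves out of its summaries "AEs starting more than 70 days following the last dose of study drug for subjects on ADA", with 30 days for upadacitinib and placebo.

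For the long-term rates, SAP 10.2.2.1 states that "the numerator of the overall rate will be the total number of TEAEs reported for the event" and that "the denominator of the rates will be the total number of days exposed to study drug summed across all treated subjects divided by 365.25". Sections 10.2.2.2 and 10.2.2.3 use the same construction by system organ class and preferred term, and for events of special interest (AESI). Section 10.2.2.1 also plans a point estimate and 95% confidence interval for the treatment difference in AESI rates.

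Three further pieces of text bear on the point:

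- For exposure, SAP 10.2.2 refers the reader to Section 6.0, which covers demographics and baseline data. Exposure is in Section 8.1. That section gives an end rule only for a switch, where "the exposure under the previous study drug ends on the day before". It gives none for the last drug a subject takes.
- SAP 10.1.3 assigns each long-term event to the treatment the subject was exposed to when it occurred.
- The analyses that ignore the 30- or 70-day limit (SAP 10.2.1.1 and 10.2.1.2) are short-term tables by randomized group. Nothing similar is planned for the long-term rates.

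**The concern.** A rate per patient-year needs events and time at risk to cover the same period. Here the numerator runs past the last dose and, on the plain wording, the denominator does not. Each final discontinuation contributes up to 70 uncounted days for ADA and up to 30 for upadacitinib or placebo. Every rate is then somewhat too high, and two drugs with the same true rate would not show the same reported rate.

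The AESI rate differences are what is at stake, because they are the planned between-drug comparison of long-term safety. The distortion is systematic: a larger trial makes the interval narrower but leaves the distortion in place.

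**Working it through.** The plan states no figure for this effect, so there is nothing to reproduce. The steps below size it.

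**Inputs from the documents.** Window w = 70 days (ADA) or 30 days (upadacitinib, placebo), SAP 10.2. Year = 365.25 days, SAP 10.2.2.1. Follow-up is 48 weeks plus up to 5 years, SAP 4.2. The 10% dropout rate from SAP 4.3 is borrowed as an illustrative share stopping drug.

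**Assumptions.** T = mean years on drug. f = share with a final discontinuation and a fully observed window. r = event rate off drug divided by the rate on drug. T, f and r are taken as equal in the two groups.

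**Formula.** Reported rate / true on-drug rate = 1 + r × f × w / (365.25 × T).

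**Worked case.** 26 weeks is 182 days; f = 10%; r = 1.

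- ADA: 1 + 0.10 × 70/182 = 1.038
- Upadacitinib: 1 + 0.10 × 30/182 = 1.016
- Spurious ratio: 1.0385/1.0165 = 1.022

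| Mean exposure, share stopped | ADA factor (r = 1) | Upadacitinib factor (r = 1) | Ratio, r = 1 | Ratio, r = 0.5 |
|---|---|---|---|---|
| 26 weeks, 10% | 1.038 | 1.016 | 1.022 | 1.011 |
| 26 weeks, 20% | 1.077 | 1.033 | 1.043 | 1.022 |
| 48 weeks, 10% | 1.021 | 1.009 | 1.012 | 1.006 |
| 48 weeks, 20% | 1.042 | 1.018 | 1.023 | 1.012 |
| 1 year, all | 1.192 | 1.082 | 1.101 | 1.053 |
| 3 years, all | 1.064 | 1.027 | 1.036 | 1.018 |
| 5.92 years (48 weeks + 5 years), all | 1.032 | 1.014 | 1.018 | 1.009 |

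**Against sampling error.** Take a true rate of 3.0 per 100 patient-years (an assumption), 26 weeks and 10% stopping. The reported rates are 3.0 × 1.0385 = 3.12 and 3.0 × 1.0165 = 3.05, a gap of about 0.07. With 300 ADA subjects and switches ignored, exposure is 300 × 182/365.25 ≈ 150 patient-years, or about 4.5 events. The standard error of the ADA rate alone is about √4.5/150 × 100 ≈ 1.4 per 100 patient-years. The gap is about 5% of that.

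**Effect of matching.** If the window days are added to the denominator and r = 1, the rate is 3.0 × (T + f × w/365.25) / (T + f × w/365.25) = 3.0 for either drug, and the ratio is 1.00. Counting only on-drug events over on-drug time gives the same. If r is not 1, adding the days still aligns numerator and denominator but blends on- and off-drug rates. The on-drug version does not blend them.

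**The case against.** The unequal windows are deliberate. They follow from the half-life rule in SAP 10.2, and the protocol agrees. This stands: preferring one common window would be a matter of taste, and only the missing person-time is at issue.

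The text may not produce the mismatch at all. If the attribution rule in SAP 10.1.3 is read strictly, a subject off drug is exposed to nothing and the event drops out. That reading conflicts with the definition in 10.2, and 10.2.2 says that all treatment-emergent events are counted. So the mismatch is the plain reading but not the only one, and the plan has to say which applies.

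The effect is small. This also stands, as the figures show.

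Two stronger inferences are tempting, and the documents support neither.

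- A reader might infer that the rule favours the sponsor's drug over a competitor's. Protocol Table 6 lists adalimumab as made by the sponsor or a contract manufacturer, so both drugs are the sponsor's. The direction also assumes similar discontinuation: upadacitinib would be inflated as much as ADA if its stoppers per unit of exposure were 70/30 ≈ 2.3 times as many.
- A reader might infer that the switch rule creates the same mismatch, because a subject leaving ADA gets no 70-day ADA window. At a switch, however, events and person-time both move to the new drug, and this holds for every switch, whichever drug is left. The summary in SAP 10.1.3 based on each subject's long-term drug also shows switchers apart from non-switchers. Some carry-over of early events is possible, but it is not a numerator-denominator fault.

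**Conclusion.** The point holds as a minor one. On the plain wording of SAP 10.2 and 10.2.2, the long-term rates count post-dose events without post-dose time after final discontinuation, and no planned long-term analysis would reveal it. With equal on- and off-drug rates, fully observed windows, and equal exposure and discontinuation in the two groups, ADA is raised relative to upadacitinib by about 1% to 4% in most scenarios. It reaches about 10% only if everyone has stopped and mean exposure is near one year. At half the off-drug rate, the excess is 0.6% to 5.3% across all the scenarios shown. The shares stopping, the exposure times and the rate ratio are assumptions, because the documents give none of them for this purpose. An effect of this size is unlikely to change a safety conclusion. It is still systematic and cheap to remove, and the missing end-of-exposure rule needs settling in any case.

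**What to change.** 1. Reconcile the attribution rule in SAP 10.1.3 with the definition in 10.2, so that it is clear whether post-dose events enter the long-term rates. Point the exposure reference in 10.2.2 to Section 8.1, and define there when exposure ends for the last drug taken.
2. If post-dose events stay in, add the observed post-dose days at risk to the patient-years: up to 30 or 70, truncated at last contact or switch. A fixed 30 or 70 would overcount. Under Protocol 5.1, the 70-day call for subjects who withdraw depends on their willingness, and it is not required once commercial adalimumab is started.
3. Add one sensitivity row for the AESI rate differences, using on-drug events only or a common 30-day window. A common 70-day window is sound only while dosing is double-dummy. During that time every subject receives subcutaneous study drug, and Protocol 6.1.4 collects events "until 70 days following discontinuation of subcutaneous study drug administration". After unblinding, 70-day follow-up is not assured for upadacitinib subjects who leave the study.
4. Optionally, flag events that start soon after any switch.

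The cost is SAP wording, a small change to the exposure derivation and one extra table row. No new data are needed for the on-drug or 30-day version. Reported rates would be slightly lower than under the present rule.

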10.2.1 Analysis of Short-Term Adverse Events

Two sets of analysis will be conducted for short-term adverse events, namely "safety analysis up to Week 14" and "safety analysis up to Week 26 censored at treatment switching" as outlined in Section 10.1.1 and Section 10.1.2. Adverse events will be summarized by frequency and percentages by "as treated" treatment groups of placebo, ADA 40 mg EOW and Upadacitinib 15 mg QD.

10.2.1.1 Adverse Events Overview

The number and percentage of subjects experiencing TEAEs will be summarized by "as treated" treatment group and overall for the following AE categories.

- All TEAEs
- Treatment-emergent serious adverse events (SAEs)
- Treatment-emergent severe adverse events

- TEAEs reasonably possibly related to study drug
- TEAEs of special interest
- TEAEs leading to discontinuation of study drug
- TEAE leading to death

Additional AEs may be considered for tabulation/summary based on recommendations from Clinical and Safety as deemed appropriate.

For TEAEs of special interest, the point estimate and 95% CI (using normal approximation) will be provided for the treatment difference in AE percentages.

As a sensitivity analysis, the AE overview summary will be repeated by randomized treatment groups. In this summary, all AEs with an onset date after the first dose of study drug will be included, regardless of whether the AE occurred more than 30 days (or 70 days) after the last dose of study drug.

10.2.1.2 Adverse Events by System Organ Class and Preferred Term

The number and percentage of subjects experiencing adverse events will be tabulated by SOC and MedDRA PT by "as treated" treatment groups and overall. The SOCs will be presented in alphabetical order, and the PTs will be presented in alphabetical order within each SOC.

The following summaries of adverse events will be generated:

- All TEAEs
- Treatment-emergent serious adverse events (SAEs)
- Treatment-emergent severe adverse events
- TEAEs reasonably possibly related to study drug
- TEAEs leading to discontinuation of study drug
- TEAE leading to death
- Frequent AEs (reported in 2% of subjects or more in any treatment group)

Subjects reporting more than one adverse event for a given MedDRA preferred term will be counted only once for that term (most severe incident for the severity tables and most related incident for the relationship tables). Subjects reporting more than one type of adverse event within a SOC will be counted only once for that SOC. Subjects reporting more than one type of adverse event will be counted only once in the overall total.

As a sensitivity analysis, the AE summary by SOC and PT will be repeated by randomized treatment groups. In this summary, all AEs with an onset date after the first dose of study drug will be included, regardless of whether the AE occurred more than 30 days (or 70 days) after the last dose of study drug.

10.2.1.3 TEAEs by Maximum Severity

TEAEs will also be summarized by maximum severity by "as treated" treatment group and overall. If a subject has an AE with an unknown severity, then the subject will be counted in the severity category of unknown, even if the subject has another occurrence of the same event with a severity present. The only exception is that if the subject has another occurrence of the same AE with the most extreme severity – severe. In this case, the subject will be counted under the severe category.

10.2.1.4 TEAEs by Maximum Relationship

TEAEs will also be summarized by maximum relationship to Upadacitinib and Placebo, as assessed by the investigator, by "as treated" treatment group and overall. If a subject has a TEAE with an unknown relationship, then the subject will be counted in the relationship category of "unknown," even if the subject has another occurrence of the same event with a relationship present. The only exception is if the subject has another occurrence of the same TEAE with a relationship assessment of "reasonable possibility." In this case, the subject will be counted under the "reasonable possibility" category.

10.2.1.5 Frequent ($\geq 2\%$) Adverse Events and Reasonably Possibly Related Adverse Events by System Organ Class and Preferred Term

TEAEs and reasonably possibly related AEs occurring for more than 2% of the subjects in any of the "as treated" treatment groups will be summarized by MedDRA PT in decreasing frequency separately.

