## **5.5 Treatments**

### **5.5.1 Treatments Administered**

There are two active study drugs in this study. The first is daily upadacitinib (ABT-494) and the second is ADA eow.

Upadacitinib (ABT-494) (or matching placebo) study drug will be taken orally once daily, beginning on Day 1 (Baseline), and should be taken at approximately the same time each day. The study drug can be taken with or without food. Subjects will continue their weekly stable background therapy of MTX. AbbVie will not supply MTX nor folic acid (or equivalent, such as folinic acid).

ADA (or matching placebo) will be provided as a subcutaneous injection solution in 1 mL pre-filled syringes containing ADA 40 mg/0.8 mL (or matching placebo). ADA (or matching placebo) will be subcutaneously administered eow at approximately the same time of day.

Subjects should take a dietary supplement of oral folic acid beginning on Day 1 (Baseline) throughout study participation. Folic acid dosing and timing of regimen should be followed according to the Investigator's instructions.

Subjects will receive both oral study drug QD (either upadacitinib (ABT-494) 15 mg or matching placebo) and subcutaneous study drug eow (either ADA 40 mg or matching placebo). When the last subject completes the last visit of Period 1 (Week 48), study drug assignment in both periods will be unblinded to the Sponsor and sites, and subjects will be dispensed study drug in an open-label fashion until the completion of Period 2.

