### 6.1.3 Relationship to Study Drug

The Investigator will use the following definitions to assess the relationship of the AE to the use of study drug:

Reasonable Possibility	After consideration of factors including timing of the event, biologic plausibility, clinical judgment, and potential alternative causes, there is sufficient evidence (information) to suggest a causal relationship.
No Reasonable Possibility	After consideration of factors including timing of the event, biologic plausibility, clinical judgment, and potential alternative causes, there is insufficient evidence (information) to suggest a causal relationship.

For causality assessments, events assessed as having a reasonable possibility of being related to the study drug will be considered "associated." Events assessed as having no reasonable possibility of being related to study drug will be considered "not associated." In addition, when the investigator has not reported a causality or deemed it not assessable, AbbVie will consider the event associated.

[figure not shown]
If an Investigator's opinion of no reasonable possibility of being related to study drug is given, an Other cause of event must be provided by the investigator for the serious adverse event.

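### SAP 10.2.1.4 defines the maximum-relationship table by upadacitinib and placebo, leaving out adalimumab, although the protocol and the SAP's other related-event tables refer to study drug

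*SAP*

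**What the plan says.** SAP 10.2.1.4 defines one descriptive safety table: "TEAEs will also be summarized by maximum relationship to Upadacitinib and Placebo, as assessed by the investigator". It is shown by as-treated group and overall. SAP 10.2.1 sets those groups for all short-term adverse event tables as the "treatment groups of placebo, ADA 40 mg EOW and Upadacitinib 15 mg QD". The adalimumab arm is therefore a column in the table, but adalimumab is not among the products against which relationship is judged.

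Elsewhere the documents put it differently:

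- Protocol 5.5.1: "There are two active study drugs in this study. The first is daily upadacitinib (ABT-494) and the second is ADA eow".
- Protocol 6.1.3: "The Investigator will use the following definitions to assess the relationship of the AE to the use of study drug".
- Protocol 8.1.5.1 plans relationship tables against the study drug, as the investigator assesses it.
- Protocol 8.1.5.2.1 plans the table at issue with no product named: "TEAE will also be summarized by maximum severity and by maximum relationship".
- SAP 10.2.1.1, 10.2.1.2, 10.2.2.1 and 10.2.2.2 each list "TEAEs reasonably possibly related to study drug".
- SAP 10.2.1.5 sets its rule for "TEAEs and reasonably possibly related AEs occurring for more than 2% of the subjects in any of the" as-treated groups and restricts it to no product.

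**The concern.** Every subject takes a daily tablet and an injection every other week. In the adalimumab arm the tablet is placebo and the injection is the active drug. A causality table that names upadacitinib and placebo but not adalimumab does not, read literally, ask in that arm about the active drug the subject received.

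The third Period 1 objective (Protocol 4.0, SAP 4.1) is to compare safety and tolerability of upadacitinib with placebo and with adalimumab. A table of related events by arm serves that comparison only if *related* has the same meaning in each arm and covers what each arm receives. Two things are at stake: whether the upadacitinib-adalimumab contrast in this table can be read at face value, and whether its counts will agree with the overview and with the table by system organ class and preferred term.

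**Working it through.** The plan states no figure on this point, so there is none to reproduce. The check is a comparison of texts, followed by what the literal rule would do under each way the data might be held.

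**Step 1: is adalimumab a study drug?** Yes, by Protocol 5.5.1. A row defined as related to study drug therefore covers adalimumab.

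**Step 2: which related-event summaries use which definition?**

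| Summary | Relationship to |
|---|---|
| Protocol 8.1.5.1, general plan | study drug |
| Protocol 8.1.5.2.1, maximum relationship | no product named |
| SAP 10.2.1.1, overview | study drug |
| SAP 10.2.1.2, by system organ class and preferred term | study drug |
| SAP 10.2.1.4, maximum relationship | upadacitinib and placebo |
| SAP 10.2.1.5, frequent related events | no product named |
| SAP 10.2.2.1 and 10.2.2.2, long-term rates | study drug |

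One table is out of step, and the SAP gives no reason for it.

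**Step 3: what would the literal rule do?** Two facts are needed that the documents do not settle: whether causality is recorded once or per product, and whether *placebo* in 10.2.1.4 means the placebo tablet alone or also the placebo injection.

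For arm k, let r_k be the proportion of subjects with any event related to study drug. Let s_k be the share of those subjects whose related events were all attributed to the injection alone. If injection-only attributions drop out, the table shows r_k × (1 − s_k).

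Write U for upadacitinib and A for adalimumab. The contrast the table should show is r_U − r_A. The error is the displayed contrast minus this.

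- *Case 1, recorded once for study drug.* There is no product-level field to drop. Every s_k is irrelevant and the error is 0. But a relationship to upadacitinib and placebo specifically cannot be derived from that single field, so the table's definition does not match its data.
- *Case 2, recorded per product, placebo meaning the tablet.* Injection-only attributions drop out in all three arms. Displayed contrast: r_U(1 − s_U) − r_A(1 − s_A). Error: r_A·s_A − r_U·s_U, which can take either sign. In the upadacitinib and placebo arms the lost attributions are to an inert injection; in the adalimumab arm they are to the active drug.
- *Case 3, recorded per product, placebo including the placebo injection.* Only the adalimumab arm loses injection-only attributions. Error: r_A·s_A, which is zero or positive. The adalimumab arm's related count is understated relative to the upadacitinib arm's.

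**Step 4: can size or direction be fixed?** No. The documents give no r and no s for any arm. With s_A anywhere from 0 to 1, the displayed adalimumab proportion could be anything from r_A down to 0. The sign is nil in Case 1, undetermined in Case 2 and non-negative in Case 3.

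**Step 5: do the documents point to a case?** Only weakly, and in different directions. Protocol 6.1.3 describes a single judgement against study drug, which favours Case 1. Protocol 6.1.5 refers to relatedness to the subcutaneous drug when setting malignancy reporting, and names separate reference safety documents for the two products, which suggests some product-level thinking. SAP 8.2 pairs upadacitinib with placebo for the tablets and adalimumab with placebo for the injections, which would fit the tablet reading in Case 2. None of this shows how the case report form is laid out.

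**The case against.** The strongest reply is that this is a drafting slip with no consequence. Protocol 6.1.3 reads as one causality judgement per event. If that is what the form collects, there is nothing to leave out. Even otherwise, events attributed to adalimumab still count as related in the overview, the table by system organ class and preferred term, the frequent related-event table and the long-term rates. Tolerability is also shown by summaries that ignore causality: all treatment-emergent events, serious and severe events, events that led to stopping study drug, and deaths. Events of special interest get confidence intervals for treatment differences. No hypothesis test or ranked endpoint uses the relationship table.

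Most of that stands, and it limits the point to one descriptive table. It does not remove the point. Under single recording the definition still describes something the data cannot supply. Under per-product recording the table omits the comparator's own causality judgement in the arm that receives it.

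A reader might go further and infer that the SAP nowhere counts adalimumab-attributed events as related, or that the rule makes adalimumab look better tolerated than it is. The documents support neither. The first is contradicted by the other related-event tables. The second needs per-product recording, which is not shown. To be certain of direction it also needs the reading in Case 3; under the tablet reading all three arms lose injection-only attributions.

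**Conclusion.** The definition in SAP 10.2.1.4 is wrong as written. It omits one of the trial's two active study drugs from a causality table that includes that drug's arm, and it departs from Protocol 5.5.1, 6.1.3, 8.1.5.1 and 8.1.5.2.1 and from the SAP's own 10.2.1.1, 10.2.1.2 and 10.2.2. This conclusion rests on the text alone.

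The consequence is conditional. With per-product causality, events attributed only to adalimumab would not reach *reasonable possibility* in this table. It would not fairly compare related events between upadacitinib and adalimumab, and it could disagree with the overview and the table by system organ class and preferred term. With a single causality field no event is lost and only the wording is at fault. Size and direction cannot be derived from the documents. Efficacy inference and the other related-event tables are untouched. It is a small defect that is worth correcting because it bears on a stated comparison and costs almost nothing to remove.

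**What to change.** In SAP 10.2.1.4, replace the reference to upadacitinib and placebo with *relationship to study drug*. If causality is collected per product, add that this is the maximum over the oral product (upadacitinib or its placebo) and the subcutaneous product (adalimumab or its placebo), applied identically in every arm. That matches the definition in 10.2.1.1, 10.2.1.2 and 10.2.2, which need no change of wording; 10.2.1.5 carries no restriction and needs none either.

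The cost is one phrase and, if causality is per product, one derivation rule. No new data are needed. The sponsor should check the case report form to see which situation applies.

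A separate matter in the same paragraph can be settled at the same time: 10.2.1.4 generally places events of unknown relationship in their own category, whereas under Protocol 6.1.3 the sponsor treats unreported or unassessable causality as associated.
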